4.4.2.1.1 Statistical Hypothesis, Model and Method of Analysis

The following null and alternative hypotheses will be evaluated:

- H_0 : There is no difference between baseline and week 8
- H_1 : There is a difference between baseline and week 8

The following study product comparisons will be analyzed:

- For Experimental Dentifrice 1, baseline versus week 8
- For Experimental Dentifrice 2, baseline versus week 8

The change from baseline in the mean VITA shade score will be analysed using a MMRM. Fixed effects will be included for smoking status, baseline Total MLSI (AxI) stratification (< 45 or ≥ 45), study product, visit and study product x visit interaction. The baseline mean VITA shade score will be included as a covariate. Subject will be included as a repeated measure with unstructured covariance matrix. Kenward Rogers degrees of freedom approach will be applied. The least square means for each study product at week 8 will be presented based on observed margins and used to test for a non-zero change from baseline. If unstructured covariance matrix does not converge, compound symmetry covariance matrix will be used.

Using the above model, the adjusted mean change from baseline in the mean VITA shade score will be reported by study product group along with 95% CIs and p-values testing for a non-zero change from baseline will be provided in Table 14.2.3.2.1. For each Experimental Dentifrice, only adjusted p-values following the graphical approach (see [Figure 4-1](#)) will be presented. Significance testing will be conducted at the two-sided 5% significance level.

The assumption of normality and homogeneity of variance in the MMRM will be investigated. In case of violation of these assumptions, a suitable nonparametric test (the Van Elteren test, adjusted for the randomization stratification) will be performed for each comparison at week 8 and results will be provided to support the MMRM results.

4.4.2.1.2 Supportive Analyses

A PP analysis will be performed on the change from baseline in the mean VITA shade score if there is more than 10% difference in the number of subjects between the PP and mITT

populations. A decision on whether a PP analysis will be performed will be made prior to study unblinding (release of the randomization codes).

A summary of the mean VITA shade will be presented for the PP Population in Table 14.2.3.1.2. Statistical analysis of the mean VITA shade score will be presented for the PP population in Table 14.2.3.2.2. In addition, the mean profiles of the mean VITA shade score (Figure 14.2.2.2) at each time point will be plotted by study product for all subjects in the PP Population.

4.4.2.2 Secondary Efficacy Endpoint 2

The Secondary Efficacy Endpoint 2 will be the change from baseline in mean Total MLSI (A×I) score at week 8 and the comparison of each Experimental Dentifrice to the Reference Dentifrice.

4.4.2.2.1 Statistical Hypothesis, Model and Method of Analysis

The following null and alternative hypotheses will be evaluated:

- H_0 : There is no treatment difference
- H_1 : There is a treatment difference

The following study product comparisons will be analyzed:

- Experimental Dentifrice 1 versus Reference Dentifrice at week 8
- Experimental Dentifrice 2 versus Reference Dentifrice at week 8

The results for this endpoint will be obtained from the MMRM detailed in [Section 4.4.1.1](#). Mean differences between each Experimental Dentifrice compared to the Reference Dentifrice in the change from baseline in mean Total MLSI (A×I) score at week 8 will be presented along with 95% CIs and adjusted p-values (following the graphical approach in [Figure 4-1](#)) in Table 14.2.2.2.1. Significance testing will be conducted at the two-sided 5% significance level.

The assumption of normality and homogeneity of variance in the MMRM will be investigated. In case of violation of these assumptions, a suitable nonparametric test (the Van Elteren test, adjusted for the randomization stratification) will be performed for each comparison at week 8 and results will be provided to support the MMRM results.

4.4.2.3 Secondary Efficacy Endpoint 3

The Secondary Efficacy Endpoint 3 will be the change from baseline in mean VITA shade score at week 8 and the comparison of each Experimental Dentifrice to the Reference Dentifrice.

4.4.2.3.1 Statistical Hypothesis, Model and Method of Analysis

The following null and alternative hypotheses will be evaluated:

- H_0 : There is no treatment difference

- H_1 : There is a treatment difference

The following study product comparisons will be analyzed:

- Experimental Dentifrice 1 versus Reference Dentifrice at week 8
- Experimental Dentifrice 2 versus Reference Dentifrice at week 8

The results for this endpoint will be obtained from the MMRM detailed in [Section 4.4.2.1.1](#). Mean differences between each Experimental Dentifrice compared to the Reference Dentifrice in the change from baseline in mean VITA shade score at week 8 will be presented along with 95% CIs and adjusted p-values (following the graphical approach in [Figure 4-1](#)) in Table 14.2.3.2.1. Significance testing will be conducted at the two-sided 5% significance level.

The assumption of normality and homogeneity of variance in the MMRM will be investigated. In case of violation of these assumptions, a suitable nonparametric test (the Van Elteren test, adjusted for the randomization stratification) will be performed for each comparison at week 8 and results will be provided to support the MMRM results.

4.4.2.4 Secondary Efficacy Endpoint 4

The Secondary Efficacy Endpoint 4 will be the change from baseline in mean Total MLSI (A×I) score at week 4 for each study product and the comparison of each Experimental Dentifrice to the Reference Dentifrice.

4.4.2.4.1 Statistical Hypothesis, Model and Method of Analysis

The results for this endpoint will be obtained from the MMRM detailed in [Section 4.4.1.1](#). The same results as presented for the week 8 analysis (see [Sections 4.4.1.1](#) and [Section 4.4.2.2](#)) will also be presented for week 4, however only unadjusted p-values will be presented.

4.4.2.5 Secondary Efficacy Endpoint 5

The Secondary Efficacy Endpoint 5 will be the change from baseline in mean VITA shade score at week 4 for each study product and the comparison of each Experimental Dentifrice to the Reference Dentifrice.

4.4.2.5.1 Statistical Hypothesis, Model and Method of Analysis

The results for this endpoint will be obtained from the MMRM detailed in [Section 4.4.2.1.1](#). The same results as presented for the week 8 analysis (see [Section 4.4.2.1](#) and [Section 4.4.2.3](#)) will also be presented for week 4, however only unadjusted p-values will be presented.

4.4.2.6 Secondary Efficacy Endpoint 6

The Secondary Efficacy Endpoint 6 will be the change from baseline in the mean site MLSI (A×I) score at weeks 4 and 8 (Gingival sites, Interproximal sites, and Body sites).

The mean Interproximal MLSI (A×I) score for each subject at each visit is calculated as the mean MLSI (A×I) score over all interproximal (Mesial + Distal) sites on the facial surfaces of the six maxillary anterior teeth and six mandibular anterior teeth, and the lingual surfaces of the six mandibular anterior teeth.

The mean Gingival MLSI (A×I) and mean Body MLSI (A×I) score for each subject at each visit is calculated as the respective mean MLSI (A×I) score over Gingival or Body sites on the facial surfaces of the six maxillary anterior teeth and six mandibular anterior teeth, and the lingual surfaces of the six mandibular anterior teeth.

Descriptive statistics (n, mean, SD, Standard Error [SE], median, minimum, and maximum) will be presented for each site MLSI (A×I) score at each assessment time point (absolute and change from baseline) in Table 14.2.4.1 for all subjects in mITT Population by study product.

4.4.2.6.1 Statistical Hypothesis, Model and Method of Analysis

The same MMRM model detailed in [Section 4.4.1.1](#) for the mean Total MLSI (A×I) will be fitted separately for each mean site MLSI (A×I) score (Gingival sites, Interproximal sites, Body sites) but instead using the respective baseline mean site MLSI (A×I) score as a covariate. The same results as presented for the mean Total MLSI (A×I) score (see [Section 4.4.1.1](#), [Section 4.4.2.2](#) and [Section 4.4.2.4](#)) will be presented for each mean site MLSI (A×I) score in Table 14.2.4.2.

The assumption of normality and homogeneity of variance in the MMRM will be investigated. In case of violation of these assumptions, a suitable nonparametric test (the Van Elteren test, adjusted for the randomization stratification) will be performed for each comparison at weeks 4 and 8 and results will be provided to support the MMRM results.

4.4.2.7 Secondary Efficacy Endpoint 7

The Secondary Efficacy Endpoint 7 will be the change from baseline in the mean Total MLSI (A) and the mean Total MLSI (I) at 4 and 8 weeks.

The mean Total MLSI (A) and mean Total MLSI (I) score for each subject at each visit is calculated as the respective mean MLSI (A) or mean MLSI (I) score over all gingival, body, mesial and distal sites on the facial surfaces of the six maxillary anterior teeth and six mandibular anterior teeth, and the lingual surfaces of the six mandibular anterior teeth.

Descriptive statistics (n, mean, SD, Standard Error [SE], median, minimum, and maximum) will be presented for the mean Total MLSI (A) and the mean Total MLSI (I) scores at each assessment time point (absolute and change from baseline) in Table 14.2.5.1 for all subjects in mITT Population by study product.

4.4.2.7.1 Statistical Hypothesis, Model and Method of Analysis

The same MMRM model detailed in [Section 4.4.1.1](#) for the mean Total MLSI (A×I) will be fitted separately for mean Total MLSI (A) score and mean Total MLSI (I) score but instead

GlaxoSmithKline Consumer Healthcare Confidential

CCI ██████████ Statistical Analysis Plan Template v6.0

Page 25 of 37

using the baseline mean Total MLSI (A) and baseline mean Total MLSI (I) score as respective covariates. The same results as presented for the mean Total MLSI (A×I) score (see [Section 4.4.1.1](#), [Section 4.4.2.2](#) and [Section 4.4.2.4](#)) will be presented in Table 14.2.5.2.

The assumption of normality and homogeneity of variance in the MMRM will be investigated. In case of violation of these assumptions, a suitable nonparametric test (the Van Elteren test, adjusted for the randomization stratification) will be performed for each comparison at weeks 4 and 8 and results will be provided to support the MMRM results.

4.4.3 Exploratory Efficacy Variables

There will be no adjustment for multiplicity in the analyses for exploratory efficacy variables.

4.4.3.1 Exploratory Efficacy Variable 1

Exploratory variables are Change from baseline in Mean VITA EasyShade color co-ordinates (L^* , a^* , b^* , WI_D) and ΔE^* determined using the VITA EasyShade instrument at weeks 4 and 8.

VITA EasyShade color coordinates (L^* , a^* , b^*) will be measured instrumentally for the facial surfaces of the four central and lateral maxillary incisors (tooth numbers 7-10) using the VITA EasyShade instrument.

The collected data will be used to calculate the ΔE^* and WI_D values as:

$\Delta E^* = \text{Square root} (\Delta L^{*2} + \Delta a^{*2} + \Delta b^{*2})$, where ΔL^* , Δa^* , Δb^* are respective change from baseline values. Since ΔE^* is calculated as change from baseline. There will be no change from baseline separately for analysis.

$$WI_D = 0.511L^* - 2.324a^* - 1.100b^*$$

The mean VITA EasyShade color co-ordinate for $L^*/a^*/b^*/WI_D$ score for each subject at each visit is calculated as the respective mean $L^*/a^*/b^*/WI_D$ score over all facial surfaces of the four central and lateral maxillary incisors (tooth numbers 7-10). Change from baseline values will be used for analysis.

The mean VITA EasyShade color co-ordinate for ΔE^* score for each subject at each visit is calculated as the mean ΔE^* score over all facial surfaces of the four central and lateral maxillary incisors (tooth numbers 7-10). Derived ΔE^* values will be used for analysis directly since ΔE^* is calculated as change from baseline already and only derived at post-baseline visits.

Descriptive statistics (n, mean, SD, SE, median, minimum, and maximum) will be presented for each mean VITA EasyShade color co-ordinates (L^* , a^* , b^* , and WI_D) (absolute and change from baseline) and post-baseline ΔE^* score at each assessment time point in Table 14.2.6.1 for all subjects in mITT Population by study product. Raw means (\pm SE) of Mean VITA EasyShade color co-ordinates (L^* , a^* , b^* , WI_D and ΔE^*) scores at each time point will be plotted by study product in Figure 14.2.3 respectively for all subjects in mITT population.

Individual Mean VITA EasyShade color co-ordinates (L^* , a^* , b^* , WI_D and derived ΔE^*) score data will be listed for each subject by visit and study product group in Listing 16.2.6.3 for all randomized subjects.

4.4.3.1.1 Statistical Hypothesis, Model and Method of Analysis

Using the same MMRM model mentioned in [Section 4.4.2.1.1](#) (replaced with the respective baseline covariate for all apart from ΔE^* for which baseline L^* , a^* , and b^* covariates will be used) for each color co-ordinates (change from baseline in each of L^* / a^* / b^* / WI_D and derived ΔE^*), adjusted mean change from baseline, along with 95% CIs will be reported by study product group will be provided for each Mean VITA EasyShade color co-ordinates (L^* , a^* , b^* , WI_D and ΔE^*) in Table 14.2.6.2. Also, P-values testing for non-zero change from baseline will be presented for study product groups. Mean difference between study product groups, 95% CIs and p-values will be provided for each of Mean VITA EasyShade color co-ordinates (L^* , a^* , b^* , WI_D and ΔE^*) in Table 14.2.6.2. Significance testing will be conducted at the two-sided 5% significance level.

The assumption of normality and homogeneity of variance in the MMRM will be investigated. In case of violation of these assumptions, a suitable nonparametric test (the Van Elteren test, adjusted for the randomization stratification) will be performed for each comparison at weeks 4 and 8 and results will be provided to support the MMRM results.

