12.3.2 Secondary and Exploratory Analyses

There will be no adjustment for multiplicity in the analyses described in this section.

The within and between study product comparisons for the mean Total MLSI (Area x Intensity) and mean VITA shade score after 4 weeks will be based on the same respective MMRM as used for the primary analyses but based on the least square means comparisons at week 4.

The within and between study product comparisons for the other secondary and exploratory efficacy endpoints (see [Section 3](#)) after 4 and 8 weeks will be based on the same MMRM as used for the primary analyses (replacing the respective baseline for the endpoint as a covariate) and the least square means comparisons at weeks 4 and 8. These other secondary and exploratory endpoint values across the study and change from baseline will also be summarised descriptively.

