14.2 Efficacy Data Summary Tables and Figures						
	Table	14.2.1	Summary of Brushing Compliance	miITT Population	14.2.1	
	Table	14.2.2.1.1	Summary of Mean Total MLSI (A×I) Score	miITT Population	14.2.2.1.1	Yes
	Table	14.2.2.1.2	Summary of Mean Total MLSI (A×I) Score	PP Population	14.2.2.1.1	
	Table	14.2.2.2.1	Statistical Analysis of Change from Baseline in Mean Total MLSI (A×I) Score	miITT Population	14.2.2.2.1	Yes
	Table	14.2.2.2.2	Statistical Analysis of Change from Baseline in Mean Total MLSI (A×I) Score	PP Population	14.2.2.2.1	
	Table	14.2.3.1.1	Summary of Mean VITA Shade Score	miITT Population	14.2.3.1.1	Yes
	Table	14.2.3.1.2	Summary of Mean VITA Shade Score	PP Population	14.2.3.1.1	
	Table	14.2.3.2.1	Statistical Analysis of Change from Baseline in Mean VITA shade score	miITT Population	14.2.3.2.1	Yes

CSR Section	TLF	Number	Title	Population	Template	Topline
	Table	14.2.3.2.2	Statistical Analysis of Change from Baseline in Mean VITA shade score	PP Population	14.2.3.2.1	
	Table	14.2.4.1	Summary of Mean MLSI (A*I) Score by Sites (Interproximal/Gingival/Body)	miITT Population	14.2.4.1	
	Table	14.2.4.2	Statistical Analysis of Change from Baseline in Mean MLSI (A*I) Score by Sites (Interproximal/Gingival/Body)	miITT Population	14.2.4.2	
	Table	14.2.5.1	Summary of Mean MLSI Score by Area and Intensity	miITT Population	14.2.5.1	
	Table	14.2.5.2	Statistical Analysis of Change from Baseline in Mean MLSI Score by Area and Intensity	miITT Population	14.2.5.2	
	Table	14.2.6.1	Summary of Mean VITA EasyShade color co-ordinates (L*, a*, b*, WI _D and Delta E*) score	miITT Population	14.2.6.1	Yes
	Table	14.2.6.2	Statistical Analysis of Change from Baseline in Mean VITA EasyShade color co-ordinates (L*, a*, b*, WI _D and Delta E*) score	miITT Population	14.2.6.2	Yes
	Table	14.2.7.1	Intra-examiner Repeatability Analysis of MLSI Score	MLSI Repeatability Population	14.2.7.1	
	Table	14.2.7.2	Intra-examiner Repeatability Analysis of VITA Shade Score	Vita Shade Repeatability Population	14.2.7.2	
	Figure	14.2.1.1	Mean Total MLSI (A*I) Score Mean (\pm SE) Plot Over Time by Product Group	miITT Population	14.2.1.1	
	Figure	14.2.1.2	Mean Total MLSI (A*I) Score Mean (\pm SE) Plot Over Time by Product Group	PP Population	14.2.1.1	

CSR Section	TLF	Number	Title	Population	Template	Topline
	Figure	14.2.2.1	Mean VITA Shade Score Mean (\pm SE) Plot Over Time by Product Group	mITT Population	14.2.2.1	

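### The SAP tests mean ΔE* against zero within each product, but ΔE* cannot be negative, so in practice every product will come out significant

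*SAP*

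**What the plan says.** SAP 4.4.3.1 defines ΔE* as the square root of the sum of the squared ΔL*, Δa* and Δb*, which "are respective change from baseline values". Tooth-level values are averaged over the four maxillary incisors, and the average is itself the response because it "is calculated as change from baseline already and only derived at post-baseline visits".

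SAP 4.4.3.1.1 puts ΔE* into the same MMRM as L*, a*, b* and WI_D, with an adjusted mean and 95% CI by product. It then states: "Also, P-values testing for non-zero change from baseline will be presented for study product groups". It closes with "Significance testing will be conducted at the two-sided 5% significance level". The only special treatment of ΔE* is its covariates: baseline L*, a* and b* replace a baseline value of the endpoint.

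Protocol 12.3.2 has the same intention: "The within and between study product comparisons for the other secondary and exploratory efficacy endpoints" are to come from the primary-analysis model, without multiplicity adjustment. The results go into Table 14.2.6.2 ("Statistical Analysis of Change from Baseline in Mean VITA EasyShade color co-ordinates"), which SAP Appendix 1 marks as topline.

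**The concern.** A test of mean change against zero suits a signed quantity such as L* or WI_D, where no effect means an expected value of zero. ΔE* is a distance. It is zero for a tooth only when all three readings repeat exactly, and Protocol 9.2.3 takes a single reading per tooth, so reading error stays in every difference. The within-product null is therefore false before any product effect is considered. ΔE* also has no direction: lightening and darkening by the same amount give the same value.

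At stake is a topline table with a very small ΔE* p-value for every dentifrice, next to the signed measures that can show whitening. A reader could take it as support for whitening when it only shows that the instrument does not repeat exactly.

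**Working it through.** 1. Sample size. The documents give no SD or power for ΔE*, so n is taken from SAP Table 1-4: 90 evaluable per arm, from 100 × (1 − 0.10) = 90. Check of that table on its limiting comparison (VITA shade, difference 1, SD 2): the noncentrality is (1/2) × √(90/2) = 3.35, and the noncentral t gives power of 91.6% at two-sided 5% and 86.2% at 2.5%. The SAP states 91.5% and 86.1%, so its figures are reproduced.

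2. Distribution of ΔE* with no true change. Assume ΔL*, Δa* and Δb* are independent normal with mean 0 and common SD s, where s is the SD of a repeat difference. Then:
   - mean of ΔE* = 2s√(2/π) = 1.596s
   - SD of ΔE* = s√(3 − 8/π) = 0.673s
   - coefficient of variation = 0.673/1.596 = 0.42, with s cancelling.

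3. Expected t for the test against zero, n = 90.
   - Four teeth perfectly correlated: √90/0.422 = 9.487/0.422 = 22.5.
   - Four teeth independent: the coefficient of variation of the subject mean is halved to 0.211, so t = 9.487/0.211 = 45.0.
   - If all the error sat in one coordinate and the teeth were perfectly correlated, ΔE* would be half-normal: mean 0.798s, SD 0.603s, coefficient of variation 0.755, t = 9.487/0.755 = 12.6.

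4. Simulation of one arm with no true change (2,000 trials per setting unless stated). There are four teeth and one reading per visit. ΔE* is averaged per subject, and the mean adjusted for centred baseline L*, a* and b* is tested against zero at two-sided 5%. This stands in for the week 8 contrast of the MMRM. The reading-error SD per visit is an assumption, tried at 0.1, 0.5, 1 and 2 units, with between-tooth correlation of the error 0 or 0.99.
   - Rejection rate: 100% in all eight settings. The mean t was about 23 (correlation 0.99) to 45 (correlation 0). The smallest t was 18.1 and the largest p-value 4 × 10⁻³¹.
   - Mean ΔE* from error alone: 0.23, 1.13, 2.26 and 4.52 at the four error SDs. This agrees with step 2, since s = √2 × the error SD and 1.596 × 1.414 = 2.26.
   - Readings rounded to 0.1 with error SD 0.05 (1,000 trials): 100%.
   - Only 10 subjects (error SD 0.5, correlation 0.99): 100%, largest p-value 0.009.

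5. Direction. With a true L* change of −1 or +1 (error SD 0.5, between-tooth correlation 0.5, 1,000 trials each), mean ΔE* was 1.47 both times and rejection 100% both times.

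6. The other tests, with no true change, in the eight settings of step 4. The within-product test rejected in 4.6% to 6.2% of trials for L* and in 4.2% to 5.8% for WI_D. The between-product ΔE* test rejected in 4.7% to 5.8%. These are close to the nominal 5%, so the fault is confined to the within-product ΔE* test.

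7. When the test could fail to reject. With n = 90 it needs a coefficient of variation above √90/1.987 = 4.77. An example is 3 or fewer of 90 subjects with equal non-zero values and all the others exactly zero.

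**The case against.** The sentence that prescribes the p-values does not name ΔE*, and SAP 4.4.3.1 says there is no separate change from baseline for it. A programmer might leave the ΔE* p-value out, and the table shell is not in the documents. This does not remove the problem. The sentences on either side list ΔE* and point to the same table, the section exempts ΔE* only for covariates, and the remark in 4.4.3.1 merely avoids subtracting baseline twice. The natural reading is that the p-values are produced.

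The consequence is also bounded, and this stands. ΔE* is one of several exploratory variables, outside the graphical procedure and outside the success criterion in Protocol section 3, which rests on MLSI. The table also carries signed measures and a between-product ΔE* comparison with sound size. That the p-value would be read as whitening is a prediction about readers; neither document calls ΔE* a whitening measure. A significant Reference result would also warn an alert reader.

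Two practical points stand and belong in the fix. A 95% CI that excludes zero conveys the same message as the p-value, so deleting the p-value alone is not enough. Dropping a comparison planned in Protocol 12.3.2 also needs a line in SAP section 5.

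**Conclusion.** The concern holds. As written, the SAP tests a non-negative quantity against zero for each product, and the test rejects essentially always: 100% in simulation against a nominal 5%, with an expected t of about 22 to 45 at 90 subjects per product. The assumptions are normal reading error of equal size in the three coordinates and no true change. The error SD is not in the documents, but under this model it cancels from the t-statistic. The result is a practical certainty and not a strict theorem, because a failure to reject would require almost every subject to have a ΔE* of exactly zero. The between-product ΔE* comparison and the primary and key secondary results are not affected. The change should be made because the outcome of these p-values is known in advance and they would appear in a topline table.

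**What to change.** In SAP 4.4.3.1.1, restrict the within-product p-values for non-zero change to L*, a*, b* and WI_D. For ΔE*, report the adjusted mean and 95% CI by product and the Experimental versus Reference differences with their CIs and p-values. Add a sentence, repeated as a footnote to Table 14.2.6.2, that the within-product ΔE* mean includes reading error, that its interval is descriptive and not to be compared with zero, and that direction is read from L*, b* and WI_D. Record in SAP section 5 that the within-product ΔE* comparison planned in Protocol 12.3.2 is not performed.

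The cost is a few sentences of SAP text and the removal of three p-values per visit (3 products × 2 visits = 6 in all). No new data and no change in conduct are needed.
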